1.3 SCHEDULE OF ACTIVITIES (SOA)

Table 1: Schedule of Activities (Aims 1 and 3)

| | Pre-Visit Contact ¹ | Baseline | 12 Months ³ |
|--|---|-------------------------------------|------------------------|
| Contact (C)/ Visit (V)/Medical Record Review (MRR) | C1 | V1 | C2/MRR ⁵ |
| Time point, days (Visit window) | Prior to outpatient visit (≤ -1) | Within 30 days of pre-visit contact | 365 \pm 30 (C2) |
| Contact patient re: interest in study visit ¹ | X | | |
| Informed consent | | X | |
| Demographics | | X | |
| Medical history (Co-morbidities) ² | | X | |
| Vaccination status | | X | X |
| CAPTURE 5-item questionnaire | | X | X |
| CAPTURE item additional questionnaire | | X | X |
| Peak Expiratory Flow (PEF) | | X | |
| Height and weight | | X | |
| Respiratory medications review | | X | X |
| Spirometry ⁴ | | X* | |
| Respiratory symptoms, exacerbation assessment | | X | X |
| Smoking exposure history | | X | |
| Smoking cessation review ⁶ | | | X |
| COPD Assessment Test (CAT) | | X | X |
| COVID-19 Questionnaire | | X | X |
| Adverse Events | | X | |
| Medical record review Additional COVID-19 items | | | X X |

1. Optional per site recruitment preferences
2. Comorbidities including cardiovascular, respiratory and malignant disorders
3. Recorded for a subset of participants who meet any of the following criteria: 1) CAPTURE+ subjects defined as CAPTURE Score ≥ 5 or CAPTURE score of 2, 3, or 4 with a low PEF, defined as <350 L/min for males and <250 L/min for females 2) abnormal spirometry defined as post-bronchodilator FEV₁/FVC < 0.70 or FEV₁ $< 80\%$ predicted at baseline, or pre-bronchodilator FEV₁/FVC < 0.65 or FEV₁ $< 70\%$ predicted for patients who do not complete post-bronchodilator spirometry; and, 3) a random sample of approximately 5% of those who do not meet criteria 1 and 2. For participants meeting criteria 1 and 2 who cannot or choose not to complete the 12-month assessment, medical record review will still be completed. For participants meeting criteria 1 and 2 who

change medical practices and medical record review cannot be completed, patients will be contacted for completion of patient reported data.

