Primary Hypothesis 3: *Sites where basic COPD and CAPTURE education are provided to clinicians, along with patient level CAPTURE data, will have a higher probability than control sites (i.e., those receiving only basic COPD education) of meeting the composite endpoint in their CAPTURE+ patients within 12 months of baseline.* From medical record review and follow-up patient survey responses, the composite endpoint is met if one of the following is recorded: (1) referral for or completion of clinical spirometry testing, 2) new clinical diagnosis of COPD, 3) newly prescribed respiratory medication (long acting bronchodilator or anti-inflammatory for respiratory condition), 4) referral to a specialist for respiratory evaluation/ treatment, or 5) referral for or completion of pulmonary rehabilitation.

The study will enroll 50 CAPTURE practices and 50 control practices; each practice will enroll 50 patients (for a total of approximately 5,000 patients). We project that within each practice, there will be at least 5 patients previously undiagnosed with COPD who have a CAPTURE+ screening result. The primary analysis will be to compare the average proportion of CAPTURE+ patients per practice that meet the composite endpoint in the two intervention arms. For power and sample sizes computations, this is a cluster randomized trial of n=50 clusters (practices) per intervention arm with 5 CAPTURE+ patients per cluster (practice). The primary power calculation is based on comparing the average cluster sample proportion (average proportion of CAPTURE+ patients per practice meeting composite endpoint) between intervention arms. Table 9-2 displays power for a two-sample test comparing average cluster sample proportions, accounting for possible intra-cluster correlation coefficient (ICC) values of 0.05, 0.10 and 0.15 that are typically seen in cluster randomized trials of behavioral interventions (<https://www.abdn.ac.uk/hsru/research/research-tools/study-design/>). These calculations assume a type I error of 5% and that the control arm meets the composite endpoint in 5% of CAPTURE+ patients and the CAPTURE arm meets the composite endpoint in higher percentages (columns of Table 9-2). There will be variability in the actual number of CAPTURE+ patients per practice. It is standard practice to inflate the number of needed clusters by 12% to account for this extra source of variability. Therefore, our power calculations are based on 44 clusters per intervention arm.

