9.2 POPULATIONS FOR ANALYSES

Aim 1

Population used for sensitivity calculations are all enrolled patients with clinically significant COPD as defined by post-bronchodilator $FEV_1/FVC < 0.70$ in addition to either ≥ 1 exacerbation-like event (ECOPD) within the past 12 months or an $FEV_1 < 60\%$ predicted.

Population used for specificity calculations are all enrolled patients with no demonstrable COPD as determined by research spirometry conducted upon study entry, $FEV_1/FVC \geq 0.70$.

Aim 2

Clinician participants: enrolled clinicians are from 2 primary care practices in each of five US PBRN regions that do not engage in Aims 1 or 3 investigation. Eligible clinicians include primary care providers and primary care clinical non-provider support personnel.

Patient participants: enrolled as a sub-sample of Aim 1 participants at baseline. One CAPTURE patient opinion survey is administered at baseline. Aim 2 participants fulfill the inclusion, exclusion and population analysis criteria of aim 1.

Aim 3

Populations used in 2-sample comparisons of outcomes between the two intervention arms will be based on randomization group (intent-to-treat analysis).

For primary analysis of each Aim 3 outcome, the analysis population will consist of all patients with follow-up data for that outcome from both the medical record review and the patient survey administered by the COPD Foundation (section 8.2).

Secondary analyses will be performed using alternative analysis populations, including

1. All patients with outcome data from the medical record review, and
2. All patients selected for follow-up.

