For each Aim 3 outcome that is collected via both medical record review and patient survey, the primary analysis will be among patients with complete outcome data from both the medical record and patient survey. Sensitivity analyses will be conducted by imputing missing outcome data using different assumptions and applying the primary analysis method to the resulting data sets. Sensitivity analyses will include (1) imputation of negative responses (i.e., responses indicating that the outcome has not occurred) for all missing patient survey responses, followed by analysis of all patients with medical record review data; (2) imputation of positive responses (i.e., responses indicating that the outcome has occurred) for all missing patient survey responses, followed by analysis of all patients with medical record review data; and (3) multiple imputation of all missing outcome data using the observed outcomes and covariates, followed by analysis of all patients selected for follow-up.

In participants who are CAPTURE+, change in CAT score will be analyzed using mixed models with a random effect for practice. The average cluster sample proportion of patients who experience exacerbations will be compared between intervention groups using methodology similar to that used for the primary endpoint. Subject to having sufficient mortality events, survival analysis allowing for correlation of endpoints within cluster (practice) will be used to compare mortality between

intervention groups and perform multivariable analysis. We will explore differences between intervention groups in the average cluster sample rate of hospitalizations again using GEE. All additional secondary analyses will also be applied to patients with clinically significant and spirometrically defined COPD, Mild COPD, PRISM, and symptomatic non-obstruction. Practices that do not have any patients with these conditions will not contribute to analyses of these secondary endpoints, respectively.

Model selection in GEE secondary analyses will be based on statistical significance at the 0.05 level using robust sandwich estimation of variability within clusters. Model fit will be checked by comparing observed versus predicted values within predefined subgroups of interest (sex, ethnic subgroups, rural and urban location, and educational status).

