
9.5 Missing Data

Baseline data, except for spirometry measurements, are expected to have few or no missing values. Baseline spirometry measurements are expected to be missing for a small portion of patients due to patient refusal/inability, administration error, or spirometry measurements having insufficient quality. Data from the 12-month medical record review are expected to be missing for a small portion of patients (among those selected for follow-up) due to various problems accessing the medical record. Data from the 12-month patient survey are expected to be missing for a significant portion of patients due to patients not returning completed surveys.

Any missing data or data anomalies will be communicated to the site(s) for clarification/resolution. We will summarize the extent of missing data by intervention group. Patient demographics, other baseline characteristics, and available 12-month follow-up data will be compared between those with and without complete follow-up data, among those who were prospectively selected for follow-up, overall and by intervention group.

The primary analysis of the primary and secondary endpoints will be among those with complete follow-up (complete data for the relevant portions of both the chart review and follow-up survey).

For each Aim 3 endpoint that is collected via both medical record review and patient survey, sensitivity analyses will be conducted by imputing missing outcome data using different assumptions and applying the primary analysis method to the resulting data sets. Sensitivity analyses will include

1. Imputation of negative responses (i.e., responses indicating that the outcome has not occurred) for all missing patient survey responses, followed by analysis of all patients with medical record review data
2. Imputation of positive responses (i.e., responses indicating that the outcome has occurred) for all missing patient survey responses, followed by analysis of all patients with medical record review data; and
3. Multiple imputation of all missing outcome data using the observed outcomes and covariates, as described below, followed by analysis of all patients selected for follow-up.

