Multiple imputation of missing values in the baseline and 12-month follow-up data will be used to create 20 complete data sets. The set of patients included in each data set will be all of those selected for 12-month follow-up. The imputation method will be multivariate imputation by chained equations (MICE)⁶ as implemented in the R package 'mice'⁷.

Missing values of baseline spirometry FVC % predicted and FEV₁ % predicted will be imputed using linear regression models with the following predictors: age, gender, height, race, education, BMI, CAT score, asthma history, short-acting bronchodilator use, maintenance respiratory medication, and any follow-up outcomes for which baseline spirometry measurements will serve as predictors (selection of those predictors is described below). Predicted FVC and FEV₁ volumes will be calculated from the NHANES reference equations, allowing for calculation of the FVC, FEV₁, and FEV₁/FVC corresponding to the imputed % predicted values as needed.

For the purpose of organizing the imputation procedures, the 12-month follow-up outcomes will be grouped as follows:

- Pulmonary care outcomes:
 - Spirometry referral/completion
 - New diagnosis of COPD
 - New prescription for respiratory medication
 - Referral to pulmonologist or other respiratory specialist
 - Pulmonary rehab referral/completion
- Flu vaccination:
 - Flu shot recommended/ordered/administered
- Smoker-specific outcomes:
 - Counseling/recommendation for smoking cessation
 - Smoking cessation program referral/completion
 - New prescription for smoking cessation medication
 - Referral to a smoking quit line

Missing values of follow-up outcome variables, all of which will be binary (yes or no), will be imputed

using logistic regression models. For each outcome variable, the predictors will include, minimally, the following:

- All other variables from the medical record review and follow-up survey within the same group of outcomes. That is, medical record review data will be used to impute missing follow-up survey data, and follow-up survey data will be used to impute missing medical record data.
- Intervention group interacting with CAPTURE status. Intervention group must be included to avoid bias when using the imputed data to estimate the intervention effect. Interaction with CAPTURE status is included because the intervention effect is hypothesized to depend on the different recommendations associated with being classified as CAPTURE+ vs CAPTURE-.

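### The Aim 3 power tables count every CAPTURE+ patient, but the primary analysis uses only those with both chart and survey data, so the stated power is too high for the planned analysis set.

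*SAP*

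**What the plan says.** **Analysis set.** Three places limit the primary Aim 3 analysis to patients with both data sources. Protocol 9.2 says that "the analysis population will consist of all patients with follow-up data for that outcome from both the medical record review and the patient survey". Protocol 9.3.2 says that "the primary analysis will be among patients with complete outcome data from both the medical record and patient survey". SAP 9.5 says that the primary analysis "will be among those with complete follow-up (complete data for the relevant portions of both the chart review and follow-up survey".

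**Endpoint.** Any one component in either source is enough (Protocol 9.1.1.3, SAP 8.2): "From medical record review and follow-up patient survey responses, the composite endpoint is met if one of the following is recorded". Charts are still reviewed for CAPTURE+ participants "who cannot or choose not to complete the 12-month assessment, medical record review will still be completed" (footnote 3 of the Schedule of Activities).

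**Expected loss.** SAP 9.5: "Data from the 12-month patient survey are expected to be missing for a significant portion of patients". It gives no figure. SAP 13.1, Table 9, reports 248 completed surveys among 380 eligible on 25 March 2020, with 20 lost to follow-up.

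**Power.** Protocol Table 9-2 (SAP Table 5) uses 5 CAPTURE+ patients per practice and 44 practices per arm. The 44 is 50 reduced to allow for variable cluster size. SAP Table 10 uses 67 practices with 10 CAPTURE+ patients each, and again allows only for variable cluster size. Neither table has a term for missing surveys.

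**Sensitivity analyses.** SAP 9.5 and 11.2 plan three: missing survey answers set to negative, missing survey answers set to positive, and multiple imputation of everyone selected for follow-up. SAP 9.5 also says that "available 12-month follow-up data will be compared between those with and without complete follow-up data", overall and by arm.

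**The concern.** A power table should describe the set of patients on which the test is run. Here the 0.05 test is run on CAPTURE+ patients with a chart and a survey, while the tables describe all CAPTURE+ patients. The SAP itself expects a substantial share of surveys not to come back, so the gap is foreseen but not priced. SAP 13.1 calls the primary analysis well powered on the same pages that report the survey count, without using that count.

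The main consequence is for reading the result. If the trial does not reach significance, readers will use the stated power to judge whether a 10-point improvement could have been missed.

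A second question is whether non-response can distort the arm difference, and whether the planned sensitivity analyses would reveal it.

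**Working it through.** **1. Inputs.** Control rate 5%, two-sided alpha 0.05, ICC 0.05/0.10/0.15 (Protocol 9.1.1.3, SAP 8.2 and 11.1). K is the number of practices per arm and m the CAPTURE+ patients per practice. Table 9-2/5: K = 44, m = 5. Table 10: m = 10 and K = 33.5 × 0.88 ≈ 29.5, where applying the 12% allowance is my inference.

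**2. Formula.** Effective n per arm = K·m / [1 + (m − 1)·ICC], entered in a two-proportion normal test with pooled null variance and unpooled alternative variance.

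**3. Reproducing the plan with all CAPTURE+ patients analysed.** For Table 9-2/5, effective n = 220/1.20, 220/1.40 and 220/1.60 = 183, 157 and 138.

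| | +7.5 | +10 | +15 |
|---|---|---|---|
| Table 9-2/5, stated | 0.72/0.65/0.59 | 0.89/0.84/0.79 | 0.99/0.98/0.97 |
| Recomputed | 0.721/0.654/0.596 | 0.894/0.843/0.793 | 0.993/0.983/0.968 |
| Table 10, stated | 0.76/0.65/0.55 | 0.92/0.84/0.76 | >0.99/0.98/0.95 |
| Recomputed | 0.765/0.648/0.557 | 0.922/0.839/0.755 | 0.996/0.982/0.953 |

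Every cell agrees within one point, so no survey loss is built in.

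**4. Completion range.** 248/380 = 65.3% if none of the open surveys returns. (380 − 20)/380 = 94.7% if all of them do. Open surveys: 380 − 248 − 20 = 112. The count covers everyone due a survey, not only CAPTURE+ patients.

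**5. Recomputed with m multiplied by completion.** At 65.3%, m = 5 becomes 3.26, and the Table 9-2/5 effective n falls to 129, 117 and 107.

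| +10 points | Table 9-2/5 | Table 10 |
|---|---|---|
| Stated | 0.89/0.84/0.79 | 0.92/0.84/0.76 |
| 94.7% | 0.88/0.83/0.78 | 0.91/0.83/0.75 |
| 65.3% | 0.77/0.73/0.69 | 0.83/0.75/0.68 |

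For Table 9-2/5 at +10 points, intermediate values are 0.85/0.80/0.76 at 85% and 0.81/0.77/0.72 at 75%. At 65.3% and +7.5 points, Table 9-2/5 gives 0.57/0.53/0.49 and Table 10 gives 0.64/0.55/0.49. At +15 points they give 0.96/0.94/0.92 and 0.98/0.95/0.91. At +25 points both stay above 0.99.

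**6. Offset.** If 100 practices each yield 10 CAPTURE+ patients (an assumption), K = 44 and m = 6.53 at 65.3% completion give 0.945/0.897/0.843 at +10 points. That is above Table 9-2/5 at every ICC.

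**7. Non-response and the arm difference (illustration).** Assume that responders have 5% and 15%, with equal return r in both arms. The overall difference reaches zero only if the control non-responder rate exceeds the CAPTURE non-responder rate by r × 10/(1 − r) points. At r = 0.653 this is 6.53/0.347 = 18.8 points. At r = 0.947 it exceeds 100 points, so it cannot happen.

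**8. What the all-positive analysis does.** With true rates of 5% and 15%, it gives (0.653 × 0.15 + 0.347) − (0.653 × 0.05 + 0.347) = +6.5 points at equal return. With 60% return in the CAPTURE arm and 70% in control it gives 0.490 − 0.335 = +15.5. With the returns reversed it gives 0.405 − 0.430 = −2.5. It is a bound that moves strongly with return rates, and it says little about plausible rates in between.

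**The case against.** **Leaving out chart-positive non-responders is right within a complete-case analysis.** A reader might infer that dropping a patient whose chart already settles the composite is an error in itself. The documents do not support that. Specialist referral is listed only in the survey table (Protocol 8.2, SAP Table 4), so a chart-negative non-responder is undetermined. Adding back only the chart-positives would select on outcome. With 65.3% return and 50–90% of events charted (assumed), a true 15% would read as (0.15r + 0.15(1 − r)c)/(r + 0.15(1 − r)c) = 18–21%, where c is the share of events charted. This objection stands.

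**The planned analyses bring non-responders back.** All three sensitivity analyses include them. The imputation models use each patient's chart items and the term "Intervention group interacting with CAPTURE status", so they already allow intermediate, arm-specific rates under missing-at-random. This also stands. What remains untested is a departure from missing-at-random that lies between all-yes and all-no.

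**The low power figures rest on a snapshot, and the yield was better than designed.** Five CAPTURE+ patients per practice was a floor, and SAP 13.1 describes 10 as the current state. Table 10 is a March 2020 contingency calculation rather than the final design. This limits the size of the point. It does not remove it, because both tables still describe an analysis set that the plan does not use.

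**Conclusion.** The point holds for the power tables. At the stated cluster numbers and sizes, stated power is too high for the planned analysis set. At +10 points the overstatement is about 1 percentage point at 94.7% completion and about 8 to 12 at 65.3%, depending on table and ICC. The calculation assumes that completion is the same in every practice and that no charts are missing. Uneven completion or missing charts would lower power somewhat further.

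Two stronger readings are not supported:

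- **That the trial is underpowered.** Neither the final number of CAPTURE+ patients nor the final completion rate is in the documents, and a plausible yield offsets the loss.
- **That the primary result is biased.** The SAP selects imputation predictors related to both missingness and outcome, and lists several for the pulmonary survey items. That makes purely random non-response doubtful. However, the screen pooled the arms and covered everyone selected for follow-up, so it shows nothing about the arm difference.

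The gap in the sensitivity analyses is narrow: no planned analysis varies non-responder rates by arm away from missing-at-random without going to the extremes.

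**What to change.** 1. **Restate power.** Give Protocol Table 9-2 / SAP Table 5 and SAP Table 10 with the expected number of analysable CAPTURE+ patients per practice, over about 65–95% survey completion.
2. **Add a tipping-point analysis** to SAP 9.5 and 11.2. Vary the outcome rate of chart-negative non-responders separately by arm, keep any charted event as a success, and report the combinations at which the conclusion changes.

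Making multiple imputation the primary analysis is an option for the sponsor to weigh, not a required correction. It would use all patients selected for follow-up, but the confirmatory result would then rest on missing-at-random. If complete-case stays primary, a sentence giving the reason would help. Chart-positive non-responders should not simply be added to the complete cases.

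The cost is a wording change, a lower stated power and a little more analysis. Restating power does not change enrolment; its use is in reading a null result. SAP 9.2 requires decisions to be documented before unblinding and database lock, so both changes belong before then.

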8.2 LONGITUDINAL FOLLOW-UP ASSESSMENTS AND DATA COLLECTION

For Aim 3, the follow-up efficacy assessments are collected from the time of baseline to 12 months in selected cohorts (as described in section 4.1). Medical record abstractions completed by PBRN coordinators and participant questionnaires administered by study team members from the COPD Foundation are used.

Data collected from medical record include:

| | |
|--|--|
| All participants undergoing 12-month follow-up as described in section 4.1 | Current Smokers Only |
| Clinical spirometry ordered or administered | Smoking cessation counseling |
| New recorded clinical diagnosis of COPD | Formal smoking cessation program referral/completion |
| New prescription for respiratory medication (long acting bronchodilator, inhaled steroids) | New prescription for smoking cessation medication |
| Exacerbation like event assessment (hospital, ED, minute clinic, antibiotic/steroid prescription/administration) | Referral to a smoking quit line |
| Vaccination status | |
| Formal pulmonary rehabilitation program referral/completion | |
| Data related to COVID-19 confirmed and suspected cases | |

Data from clinical visits to be collected at follow-up by telephone, secure web-based server, or mail-based methodologies directly from participants and administered by COPD Foundation study personnel include:

| | |
|--|--|
| All participants undergoing 12-month follow-up as described in section 4.1 | Current Smokers Only |
| Spirometry referral/completion | Referral to a smoking cessation program |
| New diagnosis of COPD | Referral to a smoking quit line |
| Referral to pulmonologist or other respiratory specialist | New prescription for smoking cessation medication |
| Exacerbation like event assessment | Over-the-counter patches/gum for smoking cessation |
| New prescription for respiratory medication (long acting bronchodilator, inhaled steroids) | |
| CAT score | |
| Attendance of pulmonary rehabilitation | |
| CAPTURE questions | |
| CAPTURE Additional Item Questionnaire | |
| COVID-19 related questions | |

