| Assess the impact of CAPTURE education and patient-level CAPTURE information on clinician interventions specific to smokers who are CAPTURE+. | Proportion of CAPTURE+ participants currently smoking at the baseline study visit who have any of the components of the Aim 3 primary endpoint or any of the following occur within 12 months of baseline (evaluated as a composite endpoint and as individual endpoints): 1) clinician counseling or recommendation for smoking cessation, 2) referral to a smoking cessation program, 3) referral to a smoking quit line, and 4) newly prescribed medication for smoking cessation. |
| Determine the impact of CAPTURE education and patient-level CAPTURE information on patient symptoms, exacerbations, hospitalizations, and mortality among CAPTURE+ patients. | In CAPTURE+ participants, change in CAT score between baseline and follow-up at 12 months after baseline, and proportion of patients who experience exacerbations, hospitalizations, or mortality within 12 months of baseline. |
| Determine the impact of CAPTURE education and patient-level CAPTURE information on identification and management of patients with respiratory burden. | All of the above endpoints for Aim 3, in the population of participants defined by each of the following instead of CAPTURE+ status: 1) clinically significant COPD, 2) spirometric COPD, 3) preserved ratio, impaired spirometry (PRISM), and 4) symptomatic non-obstructed (SNO). |
| Determine the potential impact of SARS CoV-2 infection on clinical actions taken in response to CAPTURE screening. | All of the above endpoints for Aim 3, in all of the analysis populations named above, separated into cohorts based on enrollment date and the degree to which follow-up may have been affected by the SARS-CoV-2 pandemic. |

6 Study Methods for Cluster Randomized Trial (CAPTURE Protocol Aim 3)

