| New prescription for respiratory medication (long acting bronchodilator, inhaled steroids, oral anti-inflammatory) | Formal smoking cessation program referral/completion |
| Exacerbation like event assessment (hospital, ED, minute clinic, antibiotic/steroid prescription/administration) | Referral to a smoking quit line |
| Vaccination status | |
| Formal pulmonary rehabilitation program referral/completion | |

Statistical Analysis Plan

CAPTURE

| | |
|--|--|
| Data related to COVID-19 confirmed and suspected cases | |
|--|--|

Table 4: Data from clinical visits to be collected at follow-up by telephone, secure web-based server, or mail- based methodologies directly from participants and administered by COPD Foundation study personnel includes:

| All participants undergoing 12-month follow-up as described in section 6.1 | Current Smokers Only |
|--|--|
| Spirometry referral/completion | Referral to a smoking cessation program |
| New diagnosis of COPD | Referral to a smoking quit line |
| Referral to pulmonologist or other respiratory specialist | New prescription for smoking cessation medication |
| Exacerbation like event assessment | Over-the-counter patches/gum for smoking cessation |
| New prescription for respiratory medication (long acting bronchodilator, inhaled steroids, oral anti-inflammatory) | |
| CAT score | |
| Attendance of pulmonary rehabilitation | |
| COVID-19 related questions | |

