Change in CAT score and change in number of episodes of respiratory illness requiring antibiotic/steroid treatment will be analyzed using mixed⁵ models with a random effect for practice. The average cluster sample proportion of patients who experience exacerbations will be compared between intervention groups using methodology similar to that used for the primary endpoint. Subject to having sufficient mortality events, survival analysis⁶ allowing for correlation of endpoints within cluster (practice) will be used to compare mortality between intervention groups and perform multivariable analysis. We will explore differences between intervention groups in the average cluster sample rate of hospitalizations again using GEE.

Secondary Analyses Using Single Imputation: Primary and secondary efficacy analyses of outcomes collected via both medical record review and patient survey will be repeated among patients with complete medical record review data, imputing a single value for missing outcome components from the patient survey. One analysis will impute a negative outcome (i.e., the event did not occur) for each missing survey response; another analysis will impute a positive outcome (i.e., the event did occur) for each missing survey response. Complete-data analyses described in sections 11.1 and 11.2 will be performed on each complete data set produced by imputation.

Secondary Analyses Using Multiple Imputation: Primary and secondary efficacy analyses will be repeated using data sets generated by the multiple imputation procedure described in section 9.5. Complete-data analyses described in sections 11.1 and 11.2 will be performed on each complete data set produced by multiple imputation. Parameter estimates and standard errors will be

combined across the multiply imputed data sets using the method of Rubin⁸, which is implemented by the `pool()` function in the R package ‘mice’. Specifically, for each parameter of interest, let Q_i be the parameter estimate from data set i , with associated complete-data variance U_i . Let m be the number of imputed data sets. Then

$$\bar{Q} = \frac{1}{m} \sum_{i=1}^m Q_i \text{ (the average of the } m \text{ estimates)}$$

is the overall parameter estimate. Let

$$\bar{U} = \frac{1}{m} \sum_{i=1}^m U_i \text{ (the average of the } m \text{ variances)}$$

and

$$B = \frac{1}{m-1} \sum_{i=1}^m (Q_i - \bar{Q})^2 \text{ (the variance in estimates between data sets).}$$

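### The primary exacerbation analysis drops patients who die before the 12-month survey, and the plan does not settle whether hospitalisation and mortality need a survey

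*SAP*

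**What the plan says.** The secondary endpoints at issue, in SAP Table 1 (section 5.1), include the "proportion of patients who experience exacerbations, hospitalizations, or mortality within 12 months of baseline".

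The completeness rule appears in three wordings:

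- SAP 9.5: "The primary analysis of the primary and secondary endpoints will be among those with complete follow-up", which it defines as "complete data for the relevant portions of both the chart review and follow-up survey".
- Protocol 9.2, for the primary analysis of each Aim 3 outcome: "all patients with follow-up data for that outcome from both the medical record review and the patient survey".
- Protocol 9.3.2 is narrower and opens with "For each Aim 3 outcome that is collected via both medical record review and patient survey".

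On data sources, the chart list in Protocol 8.2 has "Exacerbation like event assessment (hospital, ED, minute clinic, antibiotic/steroid prescription/administration" as one item, and SAP Table 3 repeats it. The participant survey list (Protocol 8.2 and SAP Table 4) has only "Exacerbation like event assessment". Death is an item in neither list. SAP 11.2 plans a survival analysis of mortality, "Subject to having sufficient mortality events", without naming where deaths are recorded.

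The Schedule of Activities in both documents puts the 12-month contact at day 365 ± 30. Its footnote 3 keeps the record review for CAPTURE+ and abnormal-spirometry participants who do not complete the 12-month assessment.

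**The concern.** A patient who has died cannot answer a survey. A rule that needs a survey therefore selects on survival, which happens after randomisation and is itself compared between the arms. The patients removed are likely to include some of the most severe respiratory courses, and their chart data will normally have been abstracted already. The primary exacerbation comparison becomes one among surviving survey responders, which sits poorly with the intention-to-treat statements in Protocol 9.2 and SAP 9.3.

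Neither document says what happens when a patient dies before the survey. There is no proxy survey, and death is not treated as a competing or composite event. The alternate contact in Protocol 7.3 is described only as a way of reaching the participant.

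**Working it through.** **1. The plan's own figure.** SAP Table 9 (section 13.1) reports 248 of 380 eligible participants with a completed survey at 25 March 2020, given as 65%. The modes add up (84 + 134 + 30 = 248) and 248/380 = 65.3%. The other 132 (34.7%) had no completed survey at that snapshot. The table has no line for deaths, so their share of the 132 is unknown.

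**2. The rule set against each endpoint.**

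| Endpoint | Chart item | Survey item | SAP 9.5 and Protocol 9.2 | Protocol 9.3.2 |
|---|---|---|---|---|
| Exacerbation | Listed | Listed | Survey needed | Survey needed |
| Hospitalisation | Named inside the exacerbation item | Not named | Survey needed if read broadly; the SAP's limit to relevant portions may release it | Not needed if treated as chart-only |
| Mortality | Not listed | Not listed | As for hospitalisation | Not needed |

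All three wordings exclude a patient without a survey from the primary exacerbation analysis. For the other two endpoints the wordings disagree.

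**3. What the other analyses recover.**

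- The two single-imputation analyses (SAP 9.5 and 11.2) take everyone with chart review data, so decedents with a chart return. The negative version counts their chart-recorded events. The positive version codes every missing survey response as an event. With about a third of surveys missing, that is an extreme bound.
- Multiple imputation covers everyone selected for follow-up. Its outcome groups in SAP 9.5 are pulmonary care, influenza vaccination and smoker-specific outcomes. None of the three event endpoints is listed.

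**4. Size, on assumptions.** No death or exacerbation rate is given. Let m be 12-month mortality, s the exacerbation risk in survivors and d the risk in decedents. Assume m = 0.5–3%, s = 10–20% and d = 30–80%. To isolate the effect of deaths, assume also that every decedent has chart data and no survey, and that responding survivors have the same risk as all survivors.

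- Proportion with decedents kept: (1 − m)s + md. Proportion under the rule: s. Shift: m(d − s).
- Smallest: 0.005 × (0.30 − 0.20) = 0.0005, or 0.05 points.
- Largest: 0.03 × (0.80 − 0.10) = 0.021, or 2.1 points.
- Share of patients with an exacerbation who are decedents, md / [(1 − m)s + md]: from 0.0015/0.2005 = 0.7% to 0.024/0.121 = 19.8%.

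**5. Effect on the comparison.** If m, s and d are the same in both arms, both proportions shift equally and the difference is unchanged. If only mortality differs, the hidden difference is (m₁ − m₂)(d − s):

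- 2% v 1%, d − s = 0.40: 0.4 points; d − s = 0.60: 0.6 points.
- 3% v 1%, d − s = 0.40: 0.8 points; d − s = 0.60: 1.2 points.

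**6. Number of patients.** The design figure of 5 CAPTURE+ per practice (SAP 8.2) gives 100 × 5 = 500. The 10 per practice in the March 2020 power update (SAP 13.1) would give 100 × 10 = 1,000. At 0.5–3% mortality that is between 500 × 0.005 = 2.5 and 1,000 × 0.03 = 30 deaths.

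**The case against.** The strongest reply is that the plan already holds most of the remedy. Protocol 9.2 names all patients with record-review outcomes as a secondary analysis population. For exacerbations, the negative single imputation counts decedents' chart events, which is close to what is asked for here. SAP 9.5 also compares available follow-up data between those with and without complete follow-up, by arm. The endpoints are secondary and unpowered, and SAP 9.7 says their p-values will be read with caution. Ordinary survey non-response is a much larger loss under the same rule.

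This stands as a limit on severity. It also rules out one inference that a reader might draw, that decedents vanish from every exacerbation analysis. They leave only the primary complete-case one. What remains is that the headline analysis excludes patients because of an outcome under comparison. The general statement in SAP 11.2 that secondary analyses will be repeated on multiply imputed data has no matching imputation model for these endpoints.

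Two further stronger readings are not supported:

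- **Hospitalisations are certainly lost too.** Hospital contact is named only in the chart item, so the SAP's limit to relevant portions and Protocol 9.3.2 both allow a chart-only analysis. The plan is ambiguous here, and exclusion is not established.
- **Mortality would be counted as zero.** Death is not a survey item, so arguably no relevant portion is missing. SAP 12.3 tabulates all-cause deaths by arm, and the safety population in SAP 9.3 is everyone selected for follow-up. Even if the rule were applied literally to the survival analysis, a death within the year but after an early survey (day 335 onwards) could count.

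**Conclusion.** The concern holds for exacerbations: by its stated rule, the primary complete-case analysis omits patients who die before the survey, whatever their charts show. For hospitalisation and mortality, the finding is that the wordings conflict over whether a survey is needed, and that the source of deaths for the survival analysis is not named.

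The size is modest, about 0.05 to 2.1 points on an arm's exacerbation proportion, and the between-arm difference is affected only if mortality or the event risks differ by arm. These figures rest wholly on the assumed ranges above; the documents supply no rate to replace them. The primary composite endpoint is not the subject of this point. The change is worth making because it is cheap and removes selection on survival from an analysis that is meant to follow randomised groups.

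**What to change.** Amend SAP 9.5, and align Protocol 9.2 and 9.3.2 with it:

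1. **Exacerbations.** Exempt deaths from the survey requirement. Patients who die within 12 months and have chart review data stay in the primary analysis with their chart-recorded events.
2. **Hospitalisation and mortality.** Analyse both in all patients selected for follow-up who have chart or vital-status data, with no survey requirement.
3. **Sources.** Name the data source for each of the three endpoints, including where the date of death comes from.

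The cost is a few sentences and no new visits, since the chart data are already collected for CAPTURE+ and abnormal-spirometry participants. The downside is that events known only from a survey are missed in decedents and, for hospitalisation, in survey non-responders. Survivors who do not return a survey are a separate trade-off, already covered by the planned sensitivity analyses, and need not move into the primary exacerbation analysis. If the data have already been unblinded, the revised analysis should be reported as an addition.
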